Study Design	
This study is a prospective, contralateral, single-site, single-visit unmasked evaluation of external and internal eyelid temperature after treatment with the MiBo ThermoFlo. Approximately 20 subjects will be evaluated for enrollment in the study, with a goal of a minimum of 12 subjects completed. Subjects will be randomly assigned to receive 12 minutes of MiBo ThermoFlo treatment (treatment) on 1 eye and 10 minutes of Bruder mask treatment (control) on the fellow eye.
 
See the flow chart at the end of the synopsis table for the schematic of the study visits and procedures of main observations (Figure 1).

Sample Size	Up to 20 subjects will be enrolled with a goal of a minimum of target of 12 subjects to complete
Study Duration	The study will last approximately 1.5 months and include a 1-month enrollment period
Anticipated Study Population	Individuals between the ages of 18-80 years old (inclusive) with less than grade 3 partial Meibomian glands on the Pult 5-point grading scale.

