4. STUDY DESIGN AND RATIONALE

4.1. Description of Study Design

This study is a prospective, contralateral, single-site, single-visit unmasked evaluation of external and internal eyelid temperature after treatment with the MiBo ThermoFlo. Approximately 20 subjects will be evaluated for enrollment in the study, with a goal of a minimum of 12 subjects completed. If a subject meets all eligibility criteria then the subject will be randomly assigned to 1 of 2 treatment sequences in a contralateral fashion, (1) MiBo ThermoFlo (left eye) / Bruder mask (right eye) or (2) Bruder mask (left eye) / MiBo ThermoFLo (right eye). Subjects will undergo each treatment for a period of 12 minutes for the MiBo ThermoFlo and 10 Minutes for the Bruder mask, per the manufacturer recommendations.

The study visit is expected to last approximately 2.5 hours. Subjects will undergo Meibography, tear lipid layer measurements, non-invasive tear break-up time, eyelid photography and the study treatments (MiBo ThermoFlo and Bruder mask).

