5. TEST ARTICLE ALLOCATION AND MASKING

5.1. Test Article Allocation

A computer-generated randomization scheme will be used to randomly assign subjects, in blocks of 2, to one of the two possible treatment sequences (left eye: MiBo ThermoFlo/ right eye: Bruder mask or right eye: Bruder mask/ left eye: MiBo ThermoFlo). The random scheme will be generated by site using the PROC PLAN procedure from SAS Software Version 9.4 or higher (SAS Institute, Cary, NC).

The study site must follow the randomization scheme provided and complete enrollment according to the randomization list and not pre-select or assign subjects. The randomized assignment of subjects will be performed at the first visit prior to the first fitting. The following must have occurred prior to randomization:

- Informed consent has been obtained
- Subject meets all the inclusion / exclusion criteria
- Subject history and baseline information has been collected.

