1.8	Eligibility after Baseline	All responses to Inclusion Criteria questions must be answered “yes” and all responses to Exclusion Criteria questions must be answered “no” for the subject to be considered eligible.	

Visit 1: Baseline			
Step	Procedure	Details	
		If subject is deemed to be ineligible after baseline, proceed to Final Evaluation and complete all forms.	

Visit 1: Treatment			
Step	Procedure	Details	
1.9	Eyelid Photography	The upper and lower eyelid margins of the subject will be photographed, OD, OS	Work Aid: Eyelid Photography
1.10	Tear Lipid Layer Thickness (LLT)	Measure the pre-treatment tear film LLT using the TearScience Lipiview, (OD, OS)	Work Aid: TearScience LipiView II Lipid Layer Thickness Measurement
1.11	Non-Invasive Tear Break Up Time (NITBUT)	Perform pre-treatment NITBUT using Oculus Keratograph 5 (OD, OS)	SOP_C12_Oculus Keratograph_V2
1.12	Corneal Topography	Perform pre-treatment corneal topography with the Oculus Keratograph	SOP_C12_Oculus Keratograph_V2
1.13	Thermography	Perform pre-treatment measurement of the external eyelid and palpebral conjunctival temperature for the upper and lower lids, (OD and OS)	SOP_C31_Thermography_V1.0
1.14	Randomization	Randomize treatment to eye using the randomization schedule	
1.15	MiBo ThermoFlo	Perform 12-minute MiBo ThermoFlo treatment on the eye indicated on the randomization schedule using the ThermoFlo Elite Eye Pad.	Work Aid: MiboFlo
1.16	Thermography	Immediately perform post-treatment measurement of the external eyelid and palpebral conjunctival temperature for the upper and lower lids, collecting data for the lower lid first.	SOP_C31_Thermography_V1.0
1.17	Bruder Mask	Heat the Bruder Mask per the manufacturer's instructions, measure the mask surface temperature and perform 10 minute Bruder Mask treatment on the contralateral eye.	Work Aid: Bruder Mask_V2

Visit 1: Treatment			
Step	Procedure	Details	
		Note: The Bruder Mask should be placed gently on the closed eyelids. Do not apply pressure on the mask and eye.	
1.18	Thermography	Perform post-treatment measurement of the external eyelid and palpebral conjunctival temperature for the upper and lower lids	SOP_C31_Thermography_V1.0
1.19	Tear Lipid Layer Thickness (LLT)	Measure the post-treatment tear film LLT using the TearScience Lipiview, OD, OS	Work Aid: TearScience LipiView II Lipid Layer Thickness Measurement

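### Section 5.1 prints the same eye assignment twice (MiBo left, Bruder right) and so contradicts the mirror-image pair in Section 4.1; correct the phrase and check the randomization list.

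*Combined protocol and SAP*

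**What the plan says.** Section 5.1 (Test Article Allocation) has subjects allocated in blocks of 2, by PROC PLAN, to one of two sequences, printed as "left eye: MiBo ThermoFlo/ right eye: Bruder mask or right eye: Bruder mask/ left eye: MiBo ThermoFlo". The same section binds the site to the result: "The study site must follow the randomization scheme provided and complete enrollment according to the randomization list".

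Section 4.1 (Description of Study Design) also lists two sequences. The first is MiBo left / Bruder right. The second reads "2) Bruder mask (left eye) / MiBo ThermoFLo (right eye".

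The Study Design entry of the synopsis randomizes subjects to "12 minutes of MiBo ThermoFlo treatment (treatment) on 1 eye and 10 minutes of Bruder mask treatment (control) on the fellow eye", without naming left or right. In Section 7.2, step 1.14 is "Randomize treatment to eye using the randomization schedule", step 1.15 is "Perform 12-minute MiBo ThermoFlo treatment on the eye indicated on the randomization schedule", and step 1.17 is to "perform 10 minute Bruder Mask treatment on the contralateral eye".

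Section 14.5 fits treatment sequence as a fixed effect and reports a 95% confidence interval for MiBo minus Bruder. It names no baseline or time term.

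**The concern.** The two options in 5.1 are one assignment written in two orders. The contradiction with 4.1 is explicit. The conflict with the synopsis and steps 1.14 and 1.15 is by implication: they make sense only if the eye given MiBo varies between subjects.

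The wording sits in the section that a programmer would naturally use to build the list. If it was followed literally, nothing was randomized. MiBo would be on the left eye throughout, and the only between-treatment comparison specified in 14.5 could not be told apart from a left-versus-right comparison.

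**Working it through.** **1. Distinct assignments**

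| Section | Option 1 | Option 2 | Distinct |
|---|---|---|---|
| 5.1 | L = MiBo, R = Bruder | R = Bruder, L = MiBo | 1 |
| 4.1 | L = MiBo, R = Bruder | L = Bruder, R = MiBo | 2 |

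The count of two stated in 5.1 is reproduced from 4.1 but not from the options printed in 5.1.

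**2. Could 5.1 mean order in time?** No. MiBo would still always be on the left eye, and steps 1.15 and 1.17 give MiBo first and Bruder second to every subject.

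**3. Split by eye.** Sections 4.1 and 4.3 give a target of 20 subjects and a minimum of 12 completing. A literal 5.1 list gives MiBo left/right splits of 20/0 or 12/0. The 4.1 pair in complete blocks of 2 gives 10/10 or 6/6.

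**4. Weight of a left-right difference, post-treatment data only.** Let τ be the true MiBo-minus-Bruder difference and δ a left-minus-right difference unrelated to treatment. A subject's MiBo-eye minus Bruder-eye value has expectation τ + δ if MiBo is on the left and τ − δ if it is on the right. With n_L and n_R subjects of each kind, the mean difference estimates

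τ + δ × (n_L − n_R)/(n_L + n_R).

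- Literal 5.1: (12 − 0)/12 = 1.0 and (20 − 0)/20 = 1.0.
- 4.1 pair, complete blocks: (6 − 6)/12 = 0 and (10 − 10)/20 = 0.

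**5. Can the baseline rescue it?** Step 1.13 measures both lids of both eyes before treatment. If δ is the same before and after treatment, the baseline difference between the eyes is also δ, and change from baseline removes it: δ − δ = 0. If instead the left and right lids respond differently to heat, or are measured differently after treatment, that difference is absent at baseline. It stays in the change score with weight 1.0 under a literal 5.1 list.

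**6. The same result as column ranks** (two eyes, inner and outer lid; identical for 12 and 20 subjects; sequence coded by its actual eye assignment)

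| Fixed effects | Literal 5.1 | 4.1 pair |
|---|---|---|
| Post only: intercept, sequence, treatment, location, treatment × location | 4 of 5 | 5 of 5 |
| Post only: intercept, treatment, eye | 2 of 3 | 3 of 3 |
| Pre and post: intercept, eye, post, post × MiBo | 4 of 4 | 4 of 4 |
| The row above plus post × eye | 4 of 5 | 5 of 5 |

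The first row is deficient because sequence is constant. The second and fourth are deficient because treatment and eye are the same column.

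**The case against.** **The intent is clear elsewhere.** Section 4.1 names the eyes in both arms, 5.1 itself speaks of two sequences in blocks of 2, and 14.5 presupposes a sequence term with two levels. Section 5.1 also refers to a first fitting although no lenses are fitted, which points to loosely edited template text. All of this stands and supports a drafting slip. It does not show what the list contains.

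**The harm depends on an unseen list.** Nothing in the documents says the list was coded literally, and no passage ranks 5.1 above 4.1. This also stands: the textual error is certain and the consequence is conditional.

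**Some supporting figures carry conditions.**
- Rank 4 of 5 for the 14.5 model assumes sequence is coded by its assignment. If two labels were kept for the identical assignments, the rank would be 5 of 5, with labels that distinguish nothing. Rank 2 of 3 for treatment and eye does not change.
- Blocks of 2 balance the subjects randomized, not those who complete. If 20 were randomized 10/10 and 12 completed at random (an assumption), an exact 6/6 split has probability C(10,6)²/C(20,12) = 44,100/125,970 ≈ 0.35. A 7/5 split would give weight (7 − 5)/12 ≈ 0.17, still far from 1.0.
- A list length of 20 is taken from the enrollment target; the documents do not state the length.

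**The affected contrast is not the numbered hypothesis.** Section 2.3 places MiBo versus Bruder among its other observations. That is correct, but it is also the only comparison that 14.5 specifies.

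**Conclusion.** The concern holds. Section 5.1 is wrong as printed: it gives one assignment where it claims two, and it contradicts 4.1. No alternative reading removes the conflict.

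The statistical consequence rests on one assumption that the documents cannot settle, namely that the list was generated from the 5.1 wording. In that case treatment and eye side are fully confounded in post-treatment data. Baseline temperatures could remove a stable left-right offset but not a left-right difference in response or in post-treatment measurement. The documents give no size for either, so the effect in °C is unknown. The comparison of MiBo with 40°C in 2.3 is not a between-eye contrast and is not aliased. No sample size or error rate changes. This should be corrected because the check costs almost nothing and the damage, if present, could not be fully repaired in the analysis.

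**What to change.** In Section 5.1, rewrite the second sequence so that the left eye receives the Bruder mask and the right eye receives MiBo, matching 4.1.

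Then check the generated list. Each block of 2 must contain one MiBo-left and one MiBo-right subject; a list of 20 would hold 10 of each. Correcting the text alone would not show how the list was built, so both steps are needed.

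The cost is one phrase and a review of about 20 lines, if the list matches the enrollment target. If the list proves correct, the design, sample size and analysis model stay as they are.

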5.2. Masking

Given the medical device being evaluated, masking is not possible. As such, this is an unmasked, open label trial. Subjects will be aware of the identity of the investigational product. Investigators and clinical site personnel involved in the data collection will not be masked as to the identity of the investigational product. Given the nature of the treatment, it is unlikely that the lack of masking will affect the study outcomes.

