2.2. Endpoints

The primary study endpoint is posterior eyelid temperature (palpebral conjunctiva) using the ICI-7320 infrared camera (Infrared Cameras Inc., Beaumont, TX). This metric has been selected as the ICI-7320 is FDA-approved [510(k) clearance] for use in medical imaging of any part of the body's surface. Collection of surface temperature with infrared video will allow for capture of the inner eyelid temperature while eyelids are inverted to access the palpebral conjunctiva. Other observations endpoints are Topography, Tear Lipid Layer thickness and Non-invasive Tear Break Up Time after treatment.

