4.2. Study Design Rationale

Previous work suggests that treatment with the MiBo ThermoFlo does not adequately raise Meibomian gland temperature at the inner eyelids to therapeutic levels therefore, this study explores the ability of the MiBo ThermoFlo to increase posterior eyelid temperature over 1 treatment session. A contralateral design was considered the most efficient design to assess the primary endpoint of the study. Given the nature of the treatment, masking of the investigator and the subjects is not feasible.

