Note: If you are using the capture image series option and need to stop image capture, click on the black box icon immediately to the right of the red recording icon directly beneath the active image:

11. Captured images will appear in the lower left-hand side of the screen. Click on the images to save and then click on "Save Image". To save all images, click on "Save All". Save images under a file name specific for the particular study and subject (and eye, if both eyes are evaluated).
12. Repeat Steps 6-9 above for the fellow eye.

Note: DO NOT unplug the USB cable from the camera or computer as this may affect calibration, particularly the emissivity correction (which is set to 0.98 as the surface of the human skin has a emissivity of 0.97-1.00; a value of 1.00 is a perfect radiator, or black body). To check for this, click on the Temperatures tab and select "Emissivity Correction".

D. Procedure: Data Backup

1. Data should be backed up after each subject has been completed but at least once per day.
2. Copy files requiring backup: Click on the icon "Shortcut to My Passport" which is located on the desktop.
3. Check to be sure the files have indeed been transferred to the My Passport external hard drive.

E. Procedure: Image Analysis

1. Under the File tab, select the "Load Image" option.
2. Select the area of the image to be analyzed using the options (box, circle, point, line, or none) located in the Analysis box located at left-hand margin of the screen (yellow arrow, Fig. 3).

UNIVERSITY of HOUSTON

THE OCULAR SURFACE INSTITUTE

Noncontact Infrared Thermography

3. Click the image immediately to the right and click the area where you would like to evaluate the surface temperature. The option selected (i.e., box) will show up on the image. This is called a Zone. You can also click on other areas of the image to introduce new zones or select another analysis (i.e., circle) to introduce a new zone shape to the image for surface temperature analyses within separate areas of the image. Each Zone will be designated in numerical order (see Fig. 3).
4. Use the red boxes to widen the area of analysis as needed.
5. The results of the minima and maxima surface temperature along with the standard deviation in the designed area of analysis will show at the right-hand side of the screen about midway down (green arrow, Fig. 3). Transfer data points into an Excel spreadsheet for additional analyses (i.e., statistical analyses).

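### Section 5.2 plays down the lack of masking, but the thermography SOP leaves the zone behind the primary temperature to the reader's choice and no masked reading is planned

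*Combined protocol and SAP*

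**What the plan says.** Section 5.2 declares the trial open label. On the people who gather the data it says "Investigators and clinical site personnel involved in the data collection will not be masked as to the identity of the investigational product", and it closes with "Given the nature of the treatment, it is unlikely that the lack of masking will affect the study outcomes". The only reason given is the nature of the treatment; the nature of the measurement is not discussed. Section 4.2 is similar: "Given the nature of the treatment, masking of the investigator and the subjects is not feasible". It does not consider whoever reads the images.

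Section 2.2 defines the outcome: "The primary study endpoint is posterior eyelid temperature (palpebral conjunctiva) using the ICI-7320 infrared camera". The thermography SOP in Appendix D describes how an image becomes a number. Its section C has the images saved under a name that identifies study, subject and eye. Its section E is a separate procedure that starts by reloading a saved image. The reader picks a zone shape from several options, is told to "click the area where you would like to evaluate the surface temperature", and then to "Use the red boxes to widen the area of analysis as needed". The results named at that step are the minimum, the maximum and the standard deviation within the zone.

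**The concern.** The reassurance in section 5.2 would be reasonable if the instrument returned one temperature without human choice. Under the SOP it does not. Shape, position and size of the zone are free, further zones may be added, and no landmark is set. Neither the protocol nor the SOP says which zone statistic is the endpoint. Section B of the SOP also mentions an overall surface temperature that the software can determine, but nothing designates it either.

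If a reader knows which device treated which eye, these choices can differ by device without anyone intending it. Such a difference enters the MiBo ThermoFlo minus Bruder estimate directly. The two-sided 95% interval planned in section 14.5 reflects sampling variation and would not reveal it.

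**Working it through.** The plan has no figure to reproduce: section 14.2 says that no formal sample size calculation was possible. The check is a comparison of texts plus an illustration under stated assumptions.

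**1. Does zone choice move the reading?** Yes, by logic alone. If zone A lies inside zone B, then max(B) ≥ max(A) and min(B) ≤ min(A). Widening a zone can therefore only raise or hold the maximum and lower or hold the minimum. For scale, a simulation of independent, normally distributed pixels gives an expected maximum of 1.96 within-zone SDs above the mean for 25 pixels, 2.50 for 100 and 2.97 for 400. Going from 25 to 400 pixels adds 2.97 − 1.96 = 1.01 SDs. Real neighbouring pixels are unlikely to be independent, so this shows direction, not the size to expect.

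**2. What could a device-dependent shift do to the between-eye comparison?**

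- From the documents: n = 12 (minimum completed) and n = 20 (target enrolment), section 4.3; two-sided 95% interval, section 14.5.
- Assumed: SD per eye of 0.51 to 1.0°C. The lower end is the only temperature SD in the documents (section 2.3), and it describes the untreated ocular surface, not a treated inner lid. Between-eye correlation ρ of 0 to 0.8. A fixed shift of 0.25 or 0.5°C with no true difference.
- Simplification: a paired t interval instead of the mixed model.

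Formulas: SD of the difference = SD × √(2(1 − ρ)); half-width = t(0.975, n − 1) × SD of the difference / √n; the chance that the interval excludes zero comes from the noncentral t with noncentrality shift / (SD of the difference / √n).

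First example: 0.51 × √(2 × 0.2) = 0.323, and 2.201 × 0.323 / √12 = 0.205°C. Second example: 1.0 × √2 = 1.414, and 2.201 × 1.414 / √12 = 0.899°C.

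| n | SD per eye | ρ | SD of difference | Half-width (°C) | P(excludes 0), shift 0.25°C | P(excludes 0), shift 0.5°C |
|---|---|---|---|---|---|---|
| 12 | 0.51 | 0 | 0.721 | 0.458 | 0.195 | 0.591 |
| 12 | 0.51 | 0.8 | 0.323 | 0.205 | 0.687 | 0.998 |
| 12 | 1.0 | 0 | 1.414 | 0.899 | 0.087 | 0.201 |
| 12 | 1.0 | 0.8 | 0.632 | 0.402 | 0.240 | 0.704 |
| 20 | 0.51 | 0 | 0.721 | 0.338 | 0.313 | 0.837 |
| 20 | 0.51 | 0.8 | 0.323 | 0.151 | 0.908 | 1.000 |
| 20 | 1.0 | 0 | 1.414 | 0.662 | 0.117 | 0.324 |
| 20 | 1.0 | 0.8 | 0.632 | 0.296 | 0.389 | 0.918 |

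Without a shift each probability would be 0.05. The range is wide because the inputs are assumed, and nothing in the documents says that a shift of either size would occur.

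**3. How exposed is the 40°C conclusion?** Section 1 gives a pad temperature of about 42°C and section 2.3 a loss of about 5°C to the inner lid: 42 − 5 = 37°C, which is 40 − 37 = 3°C below the threshold. That is 3 / 0.5 = 6 times the larger illustrative shift. Half-widths for a single mean, t × SD / √n with SD 0.51 to 1.0°C, are 0.324 to 0.635°C at n = 12, also well short of 3°C.

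**4. Can reading be separated from capture?** Yes. Images are stored and reloaded. If one image is taken per eye, lid, surface and time, there are 2 × 2 × 2 × 2 = 16 per subject, of which 8 are palpebral: 8 × 12 = 96 or 8 × 20 = 160 in all.

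**5. What would reveal the treatment to a reader?** In section 7.2, steps 1.15 to 1.18, MiBo ThermoFlo is always applied and imaged first and the Bruder mask second. Capture time and file order therefore identify the device, even without the randomisation list.

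**The case against.** The strongest case against has several parts.

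- **Wording.** Section 5.2 says that an effect is unlikely, not that it is impossible. This is right, and the criticism is only that no reason drawn from the measurement supports the statement.
- **The reader is not named.** One might infer that unmasked site staff draw the zones. The documents do not say so. Section 5.2 speaks of data collection, and section 15.1 sends equipment data held outside the EDC system to the sponsor for analysis. What stands is narrower: no masked reading is provided for, whoever reads.
- **No direction.** Earlier pilot data are said to show MiBo ThermoFlo falling short, which might suggest a motive for reading it low. But section 2.3 expects both devices to fall short of 40°C and expects no difference between them. The stated expectations do not predict a bias in favour of either device.
- **The camera is less precise than the shifts illustrated.** Appendix D lists its accuracy as ±1°C or 1% in one place and 2°C or 2% in another. This matters for the absolute temperature. To the extent that camera error is a common offset, it cancels between two eyes of one subject; a device-dependent reading shift does not.
- **The free zone is the more direct cause.** This is correct. Masking a reader who may still draw any zone leaves the endpoint undefined, so the zone and the statistic must be specified as well.
- **It is a pilot.** Also true, and it limits the weight of the point, but the remedy is cheap.

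**Conclusion.** The reassurance in section 5.2 is not supported by the SOP that produces the primary endpoint. The reading depends on a zone chosen by an unnamed reader, and masked reading is technically possible but not planned. Reader discretion that differs by device could bias the MiBo ThermoFlo minus Bruder difference. The size cannot be estimated from the documents. The probabilities above (0.09 to 0.69 for a 0.25°C shift at 12 subjects) rest on an assumed SD, correlation and shift, and show sensitivity only.

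A reader might infer that the 40°C conclusion is equally at risk. The protocol's own figures do not support that: they put the inner lid near 37°C, so a shift would have to approach 3°C to change the answer. That margin assumes that the 42°C and 5°C figures hold in this study. Nor should one infer that masked reading would cure everything. It cannot remove differences that arise at capture, where step 1.16 asks for measurement immediately, lower lid first, and step 1.18 states neither. The change is worth making, but the point does not invalidate the design.

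**What to change.** - **Section 5.2:** delete the closing sentence, or qualify it by saying that treatment cannot be masked but image reading can.
- **Endpoint definition:** before the first reading, fix one zone shape, one size, one anatomical landmark and one summary statistic for all palpebral images.
- **Coding:** save images under codes, with treatment, capture time and file order removed.
- **Reading:** whoever already performs the SOP image analysis, at the site or the sponsor, reads the images in shuffled order after the last subject, without the randomisation list. Lock the readings before linking them to allocation.
- **Reporting:** state who read the images. If that person also treated subjects or captured images, masking is only partial and the report should say so.
- **Capture:** reconcile steps 1.16 and 1.18 on timing and lid order.

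Sample size, alpha and the model stay as they are. The cost is file recoding and deferred reading of about 96 to 160 palpebral images, if one is taken per site. No added reader is required, since someone must do the image analysis anyway. The drawback is that readings are not available on the visit day.
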